Proposed Treatment/Study Plan:

Standard treatment post allogeneic transplant is supportive care only.

Statistical Considerations:

Preliminaries

This is a randomized, controlled phase III trial to compare azacitidine (AZA) maintenance to standard of care in patients with high risk AML/MDS who have undergone an allogeneic stem cell transplant (allotx). Patients will be randomized fairly between azacitidine and standard of care. Starting at 40 to 100 days post allotx, patients randomized to the azacitidine arm will receive 32 mg/m² for five consecutive days of each 28 day cycle and the maximum treatment will be 12 cycles. Each cycle will consist of approximately 28 days, allowing the possibility that treatment within a cycle may be delayed for up to 4 weeks due to organ toxicity or hematologic toxicity.

Group sequential design

The primary outcome for treatment evaluation will be relapse-free survival (RFS) time. A null historical RFS time of 6 months will be assumed. The goal will be to

test the hypothesis that azacitidine provides at least a 50% improvement in $m =$ median RFS, from 6 to 9 months. An accrual rate of 6 patients per month will be assumed. A two-sided group sequential procedure will be used [2] with overall type I error .05 and power .80 to detect the alternative $m = 9$ months, with up to 2 interim tests and one final test, including both outer bounds for superiority and inner bounds for futility. All tests will be based on a standardized log rank statistic, and will be performed using the following cut-offs.

No. Events	Outer Z-score cut-off to reject the null hypothesis (Superiority)	Inner Z-score cut-off to accept the null hypothesis (Futility)
71	+/- 3.7103	+/- .2438
142	+/- 2.5114	+/- 1.0268
214	+/- 1.993	+/- 1.993

The number of patients accrued (sample size) required to achieve the necessary numbers of events required by the group sequential tests will be between 213 and 246 (all to be enrolled at MDACC).

The randomization will be stratified by disease (AML, MDS, biphenotypic leukemia).

Secondary outcomes

Additional outcomes that will be recorded and analyzed will include overall survival (OS) time, acute (grade 3 or 4) graft-versus host disease, organ toxicity and hematologic toxicity.

Data analyses

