All adverse events will be cross-tabulated with treatment arm, and the rates compared using a Fisher exact test. Unadjusted RFS and OS times will be estimated using the Kaplan-Meier method. Covariate adjusted comparisons will be done using a Cox model or other appropriate time-to-event regression model to be determined by preliminary goodness-of-fit analyses.

Where Will Participants Be Enrolled:

Only at MDACC

Is this an NCI-Cancer Therapy Evaluation Protocol (CTEP)? No

Is this an NCI-Division of Cancer Prevention Protocol (DCP)? No

Estimated Accrual:

Total Accrual at MDACC: 246
Estimated monthly accrual at MDACC: 6

Accrual Comments:

Do you expect your target population to include non-english speaking participants? No

Location of Treatment:

This protocol is performed on an Outpatient basis.

Length of Stay: What is the length & frequency of hospitalization?

No hospitalization is planned under this study.

Return Visits: How often must participants come to MDACC?

Daily for 5 days of each 28 day-cycle (for drug administration). Once prior to starting the drug and once weekly for 2 weeks after drug administration is completed for labs. Pts are to receive azacitidine for no more than 1 year after the first dose.

Home Care: Specify what, if any, treatment may be given at home.

There is no home care under this study. However, local physicians, should they agree to administer the drug as prescribed here, will administer azacitidine.

Name of Person at MDACC Responsible for Data Management: [name]

Prior protocol at M. D. Anderson:

Has the Principal Investigator ever had a clinical or behavioral protocol at MDACC that accrued patients?
Yes

Data Monitoring Committee:

Is treatment assignment randomized? Yes

Is this a blinded or double-blinded study? No

Does this Protocol need data safety monitoring? Yes

Provide the name of the data safety monitoring board (DSMB) monitoring this protocol:
MDACC DMC

Does this protocol have a schedule for interim and final analysis? Yes

Please describe:

We plan to have interim analyses when accrual reaches 71 and 142 patients, and a final analysis when we complete enrollment, as described in the statistical section.

Radiation Safety:

Does this study involve the administration of radioisotopes or a radioisotope labeled agent?	No
Is the radioactive compound (or drug) FDA approved and/or commercially available?	No

Investigational New Drugs:

Does this protocol require an IND? No

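### The DMC section times the looks by patients accrued, but the cut-offs are built for 71, 142 and 214 events; followed as written, this cuts power from 80% to about 64%

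*Combined protocol and SAP*

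**What the plan says.** Statistical Considerations, Group sequential design, defines the test: "A two-sided group sequential procedure will be used", "with up to 2 interim tests and one final test, including both outer bounds for superiority and inner bounds for futility". It claims "overall type I error .05 and power .80 to detect the alternative" of a 9-month median. All tests use a standardized log-rank statistic. The table indexes its cut-offs by number of events:

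| Events | Outer cut-off (reject) | Inner cut-off (accept null) |
|---|---|---|
| 71 | ±3.7103 | ±0.2438 |
| 142 | ±2.5114 | ±1.0268 |
| 214 | ±1.993 | ±1.993 |

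The same section gives 213 to 246 as the number of patients "required to achieve the necessary numbers of events required by the group sequential tests". Patients are therefore the means of reaching the events and do not themselves trigger a look.

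The Data Monitoring Committee section, answering whether there is a schedule for interim and final analysis, says: "We plan to have interim analyses when accrual reaches 71 and 142 patients, and a final analysis when we complete enrollment". The sentence ends by pointing to the statistical section as its source. Estimated Accrual puts the total at 246.

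**The concern.** The numbers 71 and 142 appear in both places, as events in one and as accrued patients in the other. The final look has moved from 214 events to the end of enrollment. Nothing in the document says which text prevails, and the cross-reference tells the reader that they agree.

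The information in a log-rank test is governed by events. When 71 patients have been accrued, many have only just entered and most have not had an event. Applying the 71-event cut-offs then means judging futility on far less information than they were designed for. A DMC that follows the schedule addressed to it would too often stop an effective treatment, and the final test would fall short of its planned events.

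**Working it through.** **Inputs from Statistical Considerations.** "A null historical RFS time of 6 months will be assumed"; the target is "median RFS, from 6 to 9 months"; accrual is 6 per month; the cut-offs are those tabulated. Allocation is read as 1:1. Assumed, because the document does not state them: exponential times, uniform entry and no dropout.

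**1. The plan's own figures.** The hazard ratio is 6/9 = 0.667, so the log effect is ln 1.5 = 0.4055. A fixed design with two-sided 5% error and 80% power needs 4 × (1.960 + 0.842)² / 0.4055² ≈ 191 events. The 214 events are that number inflated by about 12% (214/191 = 1.12), which is reasonable for three looks with futility bounds.

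With D events the log-rank Z has mean ln 1.5 × √(D/4), and looks j < k have correlation √(Dj/Dk). The means at 71, 142 and 214 events are 1.71, 2.42 and 2.97. With the tabulated cut-offs and futility applied, power is 80.1%. Two-sided type I error is 0.050 with futility non-binding and 0.044 with it binding. The stated figures therefore reproduce with event-driven looks.

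**2. Events at the accrual-based looks.** With 3 patients per month per arm, expected events in an arm at month T are 3 × [T − (1 − e^(−λT))/λ], with λ = ln 2/6 = 0.1155 for control and ln 2/9 = 0.0770 for azacitidine. At 71 patients T = 71/6 = 11.83:

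- control: 3 × (11.83 − 6.45) = 16.2
- azacitidine: 3 × (11.83 − 7.76) = 12.2

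| Trigger | Month | Expected events | Events the cut-offs assume | Share |
|---|---|---|---|---|
| 71 patients | 11.8 | 28.4 | 71 | 40% |
| 142 patients | 23.7 | 85.1 | 142 | 60% |
| 246 patients | 41.0 | 183.0 | 214 | 85% |

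**3. First-look futility by hand.** The chance that |Z| < 0.2438 is Φ(0.2438 − μ) − Φ(−0.2438 − μ).

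- 71 events, μ = 1.71: Φ(−1.46) − Φ(−1.95) ≈ 4.6%
- 28.4 events, μ = 0.4055 × √(28.4/4) = 1.08: Φ(−0.84) − Φ(−1.32) ≈ 10.9%

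**4. All looks, under 6 vs 9 months, futility applied.**

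| Schedule | Futility stop, look 1 | Futility stop, look 2 | Power |
|---|---|---|---|
| 71/142/214 events | 4.6% | 6.4% | 80.1% |
| 71/142/246 patients | 10.9% | 15.6% | 64.5% |
| 71/142/213 patients (151 events at the end) | 10.8% | 15.6% | 60.5% |
| 71/142 patients, final at 214 events | 10.9% | 15.6% | 67.2% |
| 71/142 events, final at end of enrollment (246) | 4.6% | 6.4% | 75.6% |

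In the first two rows, rejections by look are 2.3% + 43.8% + 34.0% = 80.1% for event triggers and 0.4% + 25.0% + 39.1% = 64.5% for accrual triggers. Patient-level log-rank simulation with 15,000 trials per scenario gives 79.9% and 64.2%.

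**5. Futility ignored.** Power is 83.8% with event triggers and 77.9% with accrual triggers at 246 patients (69.8% at 213).

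**6. Type I error under the accrual schedule at 246 patients.** About 0.039 to 0.044 with futility applied and 0.053 without.

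**The case against.** The strongest reply is that this is loose wording and no rival design was intended. The DMC sentence defers to the statistical section, the numbers are the same, and the cut-off table has no row for 28 or 85 events. On that reading a careful statistician would wait for the events and no power would be lost. This may well be the intent, and it makes the loss conditional on the sentence being followed. It does not remove the contradiction: the sentence is the document's direct statement of the analysis schedule, and no text ranks it below the table.

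A second reply is that the size depends on obeying the futility bounds; without them the loss is about 6 points (83.8% to 77.9%) instead of about 16. That is correct and worth reporting. But the inner bounds are written as cut-offs for accepting the null, and the stated 80% reproduces only when they are applied, so 64% is the like-for-like figure. Even with futility ignored, 77.9% is below the stated power.

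Three smaller points also stand. Type I error is barely affected. Most of the loss comes from the interim triggers: moving the final look alone costs about 4.5 points (80.1% to 75.6%). The 213-patient row is secondary, because total accrual is given as 246 and 214 events cannot arise from 213 patients.

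**Conclusion.** The concern holds. Two current sections give different triggers for the same three looks, and the cross-reference wrongly presents them as the same. The tabulated design itself is sound. If the DMC schedule is carried out as written with the tabulated cut-offs and 246 patients, power falls from 80% to about 64%, and wrong futility stops at the two interims rise from 11% to 26% (10.9% + 15.6%).

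This rests on exponential times, medians of 6 and 9 months, 6 patients per month, 1:1 allocation, no dropout and futility bounds that are obeyed. Dropout would lower the event counts further. The harm is lost power and premature futility stopping; the false-positive rate is not materially inflated.

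**What to change.** Replace the DMC sentence with one that sets the interim analyses at 71 and 142 observed relapse-free survival events and the final analysis at 214, and that states that follow-up continues after enrollment closes. Add that if a look takes place at another event count, its bounds are recomputed from the observed information fraction with the spending function that produced the table, and name that function.

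Under the plan's assumptions the looks then fall at about months 20–21, 32–34 and 45–48, the earlier month in each pair applying under the null and the later under the alternative. With 246 patients enrolled by month 41, the final analysis comes about 4 months (null) to 7 months (alternative) after the last enrollment. The cost is a short change of wording and that follow-up, with no patients beyond the planned 246.

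This version is marked terminated, so any report of the trial should state which trigger was used for each look held and how many events were available at it.
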